11.2 Serious Adverse Events

11.2.1 Definition

A serious adverse event (SAE) is any adverse event (experience) that in the opinion of either the investigator or Boehringer Ingelheim results in **ANY** of the following:

- Death.
- A life-threatening adverse event (experience). Any AE that places a participant or participant, in the view of the Investigator or sponsor, at immediate risk of death from the reaction as it occurred. It does **NOT** include an AE that, had it occurred in a more severe form, might have caused death.
- Inpatient hospitalization or prolongation of existing hospitalization (for > 24 hours).
- A persistent or significant incapacity or substantial disruption of the ability to conduct normal life functions.
- A congenital anomaly or birth defect.
- Important Medical Event (IME) that, based upon medical judgment, may jeopardize the participant and may require medical or surgical intervention to prevent one of the outcomes listed above.
- Patients may be hospitalized for administrative or social reasons during the trial (e.g., days on which infusion takes place, long distance from home to site). These and other hospitalizations planned at the beginning of the trial do not need to be reported as an SAE.

11.2.2 Reporting Serious Adverse Events

All new SAEs occurring from the date the participant signs the study consent until 30 days after the last intervention or a new treatment is started, whichever comes first, will be reported. The RPCI SAE Source Form is to be completed with all available information, including a brief narrative describing the SAE and any other relevant information.

SAEs occurring after the 30 day follow-up period that the investigator determines to be possibly, probably or definitely related to the study intervention should be reported.

SAEs identified as an Unanticipated Problem by the Investigator must be reported. Please refer to Section 11.5 for details on reporting Unanticipated Problems.

11.3 Investigator Reporting: Notifying Boehringer Ingelheim

The following events are considered as Protocol-specified events of special interests:

Any gastrointestinal and non-gastrointestinal perforations, leakage, fistula formation, abscess.

In such case the following additional information need to be collected, documented in the respective comment field of the BI IIS SAE form and the respective narratives of the SAE. That has to be forwarded to Boehringer Ingelheim:

- Location of perforation, leakage, fistula, abscess

- Location/extent of abdominal tumor manifestations,
- Imaging and reports (CT, ultrasound, endoscopy, pathology, etc.)
- Prior surgery (location, wound healing complications)
- Concomitant diseases with GI involvement (e.g., M Crohn, vasculitis, tuberculosis, diverticulitis)
- Thromboembolic events (or predisposition)

Drug-induced liver injury is under constant surveillance by sponsors and regulators and is considered a protocol-specified adverse event of special interest (AESI). Timely detection, evaluation, and follow-up of laboratory alterations of selected liver laboratory parameters to distinguish an effect of the investigational drug from other causes are important for patient safety and for the medical and scientific interpretation of the finding.

The following are considered as protocol-specified AESI:

- An elevation of ALT and / or AST > 5 x ULN without bilirubin elevation measured in the same blood draw sample.
- An elevation of AST and/or ALT > 2.5 fold ULN combined with an elevation of bilirubin to > 1.5 fold ULN measured in the same blood draw sample.

Patients showing above laboratory abnormalities need to be followed up until the protocol specific retreatment criteria have been met and according to Appendix B of this clinical trial protocol.

Protocol-specified AESI are to be reported in an expedited manner similar to Serious Adverse Events, even if they do not meet any of the seriousness criteria.

11.3.1 SAE reporting to Boehringer Ingelheim (BI)

Upon inclusion into a trial, the patient's condition is assessed (e.g., documentation of history / concomitant diagnoses and diseases), and relevant changes from baseline are noted subsequently.

All adverse events, serious and non-serious, occurring during the course of the clinical trial (i.e., from signing the informed consent onwards through 30 days following cessation of treatment) will be collected, documented by the investigator.

The investigator shall report all SAEs and non-serious AEs which are relevant to a reported SAEs and AESIs by fax using BI IIS SAE form to BI Unique Entry Point as detailed below in accordance with the following timelines:

- within five (5) calendar days upon receipt of initial and follow-up SAEs containing at least one fatal or immediately life-threatening event
- within ten (10) calendar days upon receipt of any other initial and follow-up SAEs

Boehringer Ingelheim Pharmaceuticals, Inc
[name]
[name]
[contact]

AND NCCN at [contact] or [contact]

For each adverse event, the investigator will provide the onset date, end date, intensity, treatment required, outcome, seriousness, and action taken with the investigational drug. The investigator will determine the relationship and expectedness with the investigational drug to all AEs as defined in the listed adverse event section of Boehringer Ingelheim's (BI's) Investigator Brochure for the Product.

The investigator does not need to actively monitor patients for adverse events once the clinical trial has ended. However, if the investigator becomes aware of an SAE(s) that occurred after the patient has completed the clinical trial (including any protocol specified follow-up period), it should be reported to BI if considered relevant by the investigator.

Investigators MUST report within 5 business days upon becoming aware, to Boehringer Ingelheim ANY Serious Adverse Events, whether or not they are considered related to the investigational agent(s)/intervention.

11.4 Follow-Up for Serious Adverse Events

All related SAEs should be followed to their resolution, until the study participant is lost to follow-up, the start of a new treatment, or until the study investigator assesses the event(s) as stable or irreversible. New information will be reported when it is received.

11.5 Unanticipated Problems

11.5.1 Definition

An Unanticipated Problem (UP) is any incident, experience, or outcome that meets all of the following criteria:

- Unexpected (in terms of nature, severity, or frequency) given:
 - a) The research procedures that are described in the study-related documents, including study deviations, as well as issues related to compromise of participant privacy or confidentiality of data.
 - b) The characteristics of the participant population being studied.
- Related or possibly related to participation in the research (possibly related means there is a reasonable possibility that the incident, experience, or outcome may have been caused by the procedures involved in the research).
- Suggests that the research places participants or others at a greater risk of harm (including physical, psychological, economic, or social harm) than was previously known or recognized and if in relation to an AE is also deemed **Serious** per **Section 11.2**.

11.5.2 Reporting Unanticipated Problems

Unanticipated problem reporting will begin at the time of participant consent. The Unanticipated Problem Form will be submitted to the RPCI's Clinical Research Services (CRS) Compliance Office within 1 business day of becoming aware of the Unanticipated Problem.

When becoming aware of new information about an Unanticipated Problem, submit the updated information to CRS Compliance with an updated Unanticipated Problem Form. The site Investigator or designated research personnel will report all unanticipated problems, whether related or unrelated to the investigational agent(s) to the **IRB in accordance with their local institutional guidelines**.

12 DATA AND SAFETY MONITORING

Dose Escalation:

Phase 1 studies will be reviewed at the scheduled Roswell Park Early Phase Clinical Trials (EPCT) Program meetings and the minutes are forwarded to the IRB for review.

Phase II:

The Roswell Park Data Safety Monitoring Committee (DSMC) will assess the progress of the study, the safety data, and critical efficacy endpoints. The DSMC will review the study annually and will make recommendations that include but are not limited to; (a) continuation of the study, (b) modifications to the design (c) or termination of the study. Since the AE and SAE reports from all study sites will be sent to Roswell Park, the Roswell Park DSMC will be responsible for overall monitoring of the study.

13 STATISTICAL METHODOLOGY

The primary endpoint of the study is the rate of CTCAE Grade 2 or higher radiation pneumonitis at 6 months after completion of chemoradiation:

- To compare the rate of symptomatic radiation pneumonitis in patients who received nintedanib versus placebo.

13.1 Sample Size Determination

A maximum of 18 participants will be enrolled to the non-randomized dose escalation portion of this study. The number of participants required is a function of the unknown dose-toxicity relationship.

A maximum of 99 participants will be enrolled to the randomized Phase 2 portion of this study (excluding patients replaced due to ineligibility or inability to start therapy). Participants will be randomized in a 1:2 fashion, stratified by chemotherapy regimen (i.e., platinum with etoposide, platinum with taxane, platinum with pemetrexed) and immune therapy (i.e. durvalumab), into the placebo and nintedanib arms. Accrual is expected to take 4 years.

Evaluable patients will be any patient who receives at least one dose of study drug.

The sample size justification is based on the primary analysis: a comparison of the rate of radiation pneumonitis at 6 months after completion of chemoradiation between the placebo and nintedanib arms, stratified by chemotherapy regimen (i.e., platinum with etoposide, platinum with taxane, platinum with pemetrexed) and immune therapy exposure (i.e. durvalumab), using the one-sided Cochran-Mantel-Haenszel (CMH) exact test at a significance level of 0.05. The expected rate of Grade 2 or higher radiation pneumonitis is 30% in the placebo arm, and a decrease in this rate to 10% in the nintedanib arm would be considered clinically significant; which is equivalent to a common odds ratio (COR) of approximately 0.26.

Using a simulation based on the proposed study design; if there is no improvement in the rate of radiation pneumonitis (COR = 1.0), then there is a 59.0% chance of stopping early for futility. If the true COR is 0.26, then there is only a 10.6% chance of stopping early for futility. If the true common odds ratio is 0.26, then there is an 80.1% chance of detecting a significant reduction in the rate of Grade 2 or higher radiation pneumonitis in the nintedanib arm. If the COR is 1.0, then the chance of detecting a significant reduction is 4.2%; which can be considered the effective type-I error rate.

As of the November 2018 Amendment (Amendment #6), patients receiving durvalumab will be eligible for enrollment in the study. Since the combination of nintedanib and durvalumab has not been tested in this setting, an initial non-randomized dose escalation study will be carried out for patients treated with immune therapy (i.e. durvalumab). This dose escalation phase will follow a standard 3+3 design starting with dose level 1 (Table 1) and continuing until the MTD is identified (maximum dose level at which 1 or fewer DLTs are observed in 6 patients). A total of 3 dose levels will be explored, hence a maximum of 18 patients will be accrued to this portion of the study.

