5 STUDY DESIGN

A maximum of 18 participants will be enrolled to the Phase I non-randomized dose escalation portion of this study. See Figure 1 for the Phase 1 dose-escalation study schema.

A maximum of 99 participants will be enrolled to the randomized Phase II, double-blind, placebo-controlled portion of the study of nintedanib as prophylaxis against radiation pneumonitis in patients with advanced NSCLC. The study schema is depicted below.

[figure not shown]
All participants will sign an informed consent prior to study related tests. All participants will meet the inclusion and exclusion criteria summarized in **Section 6.1** and **Section 6.2**.

Figure 1 Phase 1 Dose-escalation Study Schema

For patients who will be receiving durvalumab consolidation treatment as standard of care prior to establishment of the recommended phase II dose of this combination, they will NOT undergo randomization (i.e. not blinded to treatment) and will receive active drug (nintedanib) on the first day of the first dose of durvalumab 10mg/kg every 2 weeks for up to 12 months.

Figure 2. Phase II Study Schema

§Patients will be stratified according to chemotherapy regimen (i.e., platinum with etoposide, platinum with taxane, platinum with pemetrexed) utilized concurrently with radiation as well as exposure to immune checkpoint inhibitor therapy.

§§An interim analysis for futility will be conducted when the first $n_1=33$ patients have completed 6-months of follow-up post-chemoradiation; that is, when the first $n_1=33$ patients are evaluable for the primary end-point (the rate of CTCAE Grade 2 or higher radiation pneumonitis at 6

months after completion of chemoradiation). If the estimated common odds ratio (COR) is greater than or equal to 0.8, then the study will stop early for futility. Otherwise, the study will continue and enroll an additional $n_2=66$ patients. Additionally, at this time the safety profile of the treatment arms may be evaluated and considered in the decision for study continuation.

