13.5 Primary Analysis

Consider a placebo controlled, randomized trial in which patients are stratified by chemotherapy regimen (i.e., platinum with etoposide, platinum with taxane, platinum with pemetrexed) and randomized (1:2 ratio) to a treatment group (placebo versus nintedanib). The primary objective of the study is to evaluate the rate of radiation pneumonitis at 6 months after completion of chemoradiation in patients with unresectable Stage II/III/oligometastatic IV NSCLC who completed chemoradiation followed by nintedanib versus placebo. The primary outcome is radiation pneumonitis status (defined as symptomatic CTC Grade 2 or higher radiation pneumonitis at 6 months after completion of chemoradiation), which is treated as a dichotomous variable.

The primary objective will be assessed using the intent-to-treat principle and a one-sided exact test about the CMH COR:

$$H_0: \theta \geq 1$$

$$H_A: \theta < 1$$

Where θ is the COR for the odds of Grade 2 or higher radiation pneumonitis in the nintedanib treated versus placebo treated populations, stratified by chemotherapy regimen (i.e., platinum with etoposide, platinum with taxane, platinum with pemetrexed). A one-sided test is performed as the rate of radiation pneumonitis is expected to decrease in the nintedanib arm over the placebo arm; that is expect to be $\theta < 1$. The critical value and corresponding rejection region for the one-sided test will be obtained using the exact methods available in SAS v9.4 and maintaining a significance level of 0.05 while accounting for the interim analysis. As of the November 2018 Amendment (Amendment #6), the primary analysis will be conducted excluding the maximum of 18 patients in the durvalumab dose escalation. As a sensitivity analysis, the primary analysis will be repeated with the 6 patients treated at the MTD level from the dose-escalation portion.

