13.8 Interim Analysis

An interim analysis for futility when the first $n_1=33$ patients have completed 6-months of follow-up post-chemoradiation; that is, when the first $n_1=33$ patients are evaluable for the primary endpoint. If the estimated COR is greater than or equal to 0.8, then the study will stop early for futility. Otherwise, the study will continue and enroll and additional $n_2=66$ patients. Additionally, at this time the safety profile of the treatment arms may be evaluated and considered in the decision for study continuation.

If the true COR is = 1.0 (no improvement in the nintedanib arm), then there is a 59.0% chance of stopping early for futility. If the true COR is 0.26, then there is only a 10.6% chance of stopping early for futility.

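### The exact CMH test named in 13.1 does not deliver the stated 80.1% power: about 63-67% at nominal 0.05, about 69-75% with a calibrated cut-off

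*Combined protocol and SAP*

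**What the plan says.** Section 13.1 sets out the design. The control assumption is "The expected rate of Grade 2 or higher radiation pneumonitis is 30% in the placebo arm", and a fall to 10% on nintedanib is the effect of interest (COR about 0.26). The arms are compared "using the one-sided Cochran-Mantel-Haenszel (CMH) exact test at a significance level of 0.05". Up to 99 patients are randomized 1:2, stratified by three chemotherapy regimens and by durvalumab exposure.

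From a simulation of this design, 13.1 reports "If the true common odds ratio is 0.26, then there is an 80.1% chance of detecting a significant reduction". For the null it reports "If the COR is 1.0, then the chance of detecting a significant reduction is 4.2" per cent. It gives futility stopping probabilities of 59.0% at COR 1.0 and 10.6% at COR 0.26.

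Section 13.8 gives the look, taken on the first 33 evaluable patients: "If the estimated COR is greater than or equal to 0.8, then the study will stop early for futility". Section 5 words it the same way, as a binding rule: "then the study will stop early for futility. Otherwise, the study will continue and enroll an additional" 66 patients.

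Section 13.5 says of the final test: "The critical value and corresponding rejection region for the one-sided test will be obtained using the exact methods available in SAS v9.4", and adds "maintaining a significance level of 0.05 while accounting for the interim analysis". It prints no numerical critical value. The stratum shares, stratum event rates and handling of zero cells at the look are not stated either.

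**The concern.** An exact test is conservative with about 20-30 events, and a futility stop can only remove rejections. With 33 against 66 patients and 30% against 10%, 80.1% therefore looked high for an exact test with a binding stop.

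The stated figure puts the risk of missing the planned effect at 100 - 80.1 = 19.9%. If true power is 69-75%, that risk is 25-31%. At nominal 0.05 it is 33-37%. A non-significant result would then be weaker evidence against a 30%-to-10% effect than 13.1 implies. Because 13.5 leaves the rejection region unprinted, the reader cannot tell which of these applies.

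**Working it through.** **Inputs.** From 13.1: 99 patients at 1:2, so 33 placebo and 66 nintedanib; rates 30% and 10%; one-sided exact CMH test at 0.05. From 13.8: look at 33 patients, so 11 and 22, then 22 and 44 more; stop if the estimated COR is 0.8 or more. Odds ratio check: (0.10/0.90)/(0.30/0.70) = 0.1111/0.4286 = 0.259, which agrees with 0.26.

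**One-stratum formulas.** Let x1 of 11 placebo and y1 of 22 nintedanib patients have events at the look. The interim odds ratio is y1(11 - x1)/[x1(22 - y1)]. The trial continues if this is below 0.8. At the end, with x of 33 and y of 66, the exact p-value is P(Y ≤ y | x + y), hypergeometric. Power is the sum of the binomial probabilities over all paths that continue and end with p at or below the cut-off c. This is full enumeration, with no simulation error. The plan does not say what happens when the interim odds ratio is undefined, so pairs below are undefined = stop / undefined = continue.

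**The plan's own stopping figures first.** At 30% vs 10%, the stop probability is 12.1% / 10.2% (stated 10.6%). At a 30% null it is 61.3% / 59.4% (stated 59.0%). These are close, so the look is being modelled much as the sponsor modelled it.

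**A bound.** Without any look, the exact test at 0.05 has 70.4% power in one stratum. A futility stop cannot raise that, so 80.1% is out of reach at nominal 0.05.

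**Power with the look, one stratum.**

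| Exact p cut-off | Power at 30% vs 10% | Type I at 30% null | Maximum type I, nulls 10-50% |
|---|---|---|---|
| 0.05 | 66.5% / 67.1% | 2.8% | 2.9% |
| 0.075 | 72.3% / 73.1% | 4.3% | 4.3% |
| 0.08 | 72.7% / 73.4% | 4.6% | 4.6% |
| 0.0854 (largest holding 5% over 10-50%) | 73.7% / 74.5% | at most 4.9% | 4.9% |
| 0.09 (holds 5% at a 30% null only) | 74.9% / 75.7% | 5.0% | 5.5% |

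Reaching 80.1% needs a cut-off of 0.150 / 0.134, where type I error is 8.1% / 7.6%.

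**Stratified simulation.** This used an exact CMH p-value, the Mantel-Haenszel COR at the look, a mean placebo rate of 30% and COR 0.26.

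- Eight scenarios with 1, 3 or 6 strata, equal or unequal shares and rates, 24,000 trials each: power 64.5-66.8% at 0.05 (type I 2.5-2.9%) and 69.9-73.0% at cut-offs 0.075-0.08 (type I 3.8-4.6%).
- Six strata with blocks within four sites (9.1 randomizes by site), 16,000 trials each: 63.2-65.6% at 0.05 and 68.6-71.9% at 0.075-0.08 (type I 3.6-4.5%).
- Cut-off calibrated to the full 5%, 40,000 trials per scenario: 72.7% with six strata, 75.0% unstratified.

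Simulation error is small: √(0.65 × 0.35/16,000) = 0.4 points.

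**Shortfall against 80.1%.** Nominal: 80.1 - 67 = 13 to 80.1 - 63 = 17 points. Calibrated: 80.1 - 75 = 5 to 80.1 - 69 = 11 points.

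**A rule that does come close.** Rejecting when the estimated COR is at most about 0.47, with the look, gives 79.4-79.5% power and 4.1% type I error at a 30% null. It is a threshold on the estimate and ignores its precision. It rejects at 10/33 vs 11/66 (COR 11 × 23/(55 × 10) = 0.46, exact p 0.098) and at 6/33 vs 6/66 (COR 6 × 27/(60 × 6) = 0.45, exact p 0.163). Its type I error is about 6.2% at a common rate of 20%, 8.4% at 15% and 12% at 10%.

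**The case against.** The strongest reply is that the pair can be produced without changing the 30% and 10%. Section 13.5 describes an exact test about the COR and refers to a critical value and rejection region. That could mean a cut-off on the estimated COR, and a cut-off near 0.47 nearly returns both figures. This stands as an explanation. A reader might infer that no rule yields 80.1% with 4.2%, or that the sponsor made an arithmetic slip; the documents support neither, and an unstated rejection region is at least as likely.

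It does not rescue 13.1. A COR threshold is not the exact CMH test at 0.05 named there. Section 1.1 puts symptomatic pneumonitis at 15-40%, and within that range the rule exceeds the 0.05 that 13.5 requires.

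Other routes are weaker. An asymptotic CMH test without the look gives 80.5% power, but with 5.1% type I error and without the planned stop. An asymptotic test with the look, at 36% placebo and COR 0.26, gives 80.0-80.3% and 4.2%, but 36% is not the stated rate and its null stop probability (62.6-63.3%) fits the stated 59.0% less well.

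It is also fair to object that the replacement figure rests on strata, rates and zero-cell handling that the plan does not give. That stands, and is why it is a range.

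**Conclusion.** Section 13.1 is wrong as written: the test it names, with the look it describes, does not have 80.1% power at 30% vs 10%. Power is about 63-67% at nominal exact p of 0.05, and about 69-75% with a cut-off calibrated to type I error of at most 0.05.

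The low ends are six strata with blocks by site. The calibrated low end comes from cut-offs of 0.075-0.08, which leave some type I error unspent. The high end is one stratum calibrated at a 30% null only; holding 5% over null rates of 10-50% lowers it to 73.7-74.5%.

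Confidence is high that 80.1% is not delivered by the named test. It is moderate on the replacement range, which depends on assumed stratum shares, stratum rates, four sites and the zero-cell convention.

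Three further inferences are not supported. The 4.2% is not an error in itself, since a calibrated exact cut-off can give about that value. The stopping probabilities are not materially misdescribed. And the plan does not inflate type I error as worded, because 13.5 requires 0.05 to be held; inflation would arise only if an unprinted COR threshold were used.

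**What to change.** Before unblinding:

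1. Re-run the simulation with its settings written down: strata (13.5 names chemotherapy regimen only, while 13.1 and 13.2 add immunotherapy exposure), stratum shares and rates, block and site scheme, and the zero-cell convention at the look.
2. Print the final rejection region in 13.5, and show that it holds type I error at or below 0.05 over plausible common event rates, with the stop treated as binding as 13.8 words it.
3. Restate the power in 13.1 from that re-run. Expect about 69-75% if the cut-off is calibrated, or about 63-67% at nominal 0.05, conditional on the stratum assumptions chosen.

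The cost is one simulation and edits to two sections, with no extra patients. The stated power becomes less favourable. A calibrated cut-off above 0.05 also depends on the stop being followed: at 0.08, for example, type I error at a 30% null is 4.6% with the look and 5.4% without it.
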